## Figure 1: VC02-101 Cohort 1 Study Schematic

Denotes possible sentinel explant (Cohort 1)

#### Figure 2: VC02-102 Cohort 1 Study Schematic

[figure not shown]
#### VC02-101 Cohort 2:

Enrollment of Cohort 2 will include up to 60 additional subjects who will be implanted with up to twelve units. Of the twelve implanted units, no more than ten (10) will be VC-02-300 units and the remainder will be VC-02-20, sentinel units. For example, if ten (10) VC-02-300 units are implanted, up to two (2) sentinels may also be implanted. The total duration of treatment may be up to two (2) years for each Cohort 2 subject. Sentinels and/or VC-02-300 units may also be explanted at various time points post-implant, but the Sponsor generally intends to explant sentinels at later time points (e.g., Week 12 or beyond) and to allow VC-02-300 units to remain implanted for the entire study duration. All remaining VC-02-300 and sentinel units will be explanted at Visit 17/Week 104.

The number of VC-02-300 units to be implanted in Cohort 2 subjects will be a data-driven decision and may vary between subjects. The Sponsor will review available C-peptide results from Cohort 1 subjects, as well as an ongoing review of C-peptide results from implanted Cohort 2 subjects, to determine the optimal number of VC-02-300 units to implant in subsequent subjects. The Sponsor generally intends to implant the least number of VC-02-300 units required to provide the intended therapeutic benefit.

There is no Cohort 2 in VC02-102.

### Figure 3: VC02-101 Cohort 2 Study Schematic

▼ Denotes possible sentinel explant (Cohort 2)

#### 32.4 Subject Compliance

Subjects who are withdrawn prematurely from the study will have the VC-02-300 units (if applicable) and sentinels explanted. If a subject withdraws from the trial and also withdraws consent for disclosure of future information in writing, no further evaluations should be performed, and no additional data should be collected. The Sponsor may retain and continue to use any data collected before withdrawal of consent.

Subjects who have not withdrawn consent, but who have been discontinued from the main study prematurely (with products explanted) will be rolled over into a 1-year, long-term, follow-up trial.

For safety reasons, all early termination procedures (including explantation procedure) as described in Visit 17/ET and Visit 18 should be performed if a subject discontinues the trial.

#### 4. GENERAL CONSIDERATIONS FOR DATA ANALYSIS

The phrase "treatment group" is used in this section to denote the number of initially implanted VC-02-300 units. If a subject has a VC-02-300 unit explanted for any reason and remains in the study, then he/she will be included in the treatment group that is described by the number of VC-02-300 units originally implanted. If no VC-02-300 units are implanted, but sentinel units are implanted, then the subject will be included in the "0 implanted VC-02-300 units" treatment group. If, during the study, the number of sentinels implanted in subjects who do not have VC-02-300 units varies widely (e.g., one subject has one sentinel unit implanted while another subject has 10 sentinel units implanted), the "zero VC-02-300 unit" treatment group may be further broken out by the number of sentinels implanted.

As the VC02-101 and VC02-102 studies collectively represent the first-in-human trial, there are no statistical hypotheses regarding treatment effects. Rather, displays and comparisons of study results – regarding safety and efficacy among the treatment groups – will primarily utilize descriptive statistics, as noted below.

Unless otherwise specified, continuous variables will be summarized by presenting the number of

non-missing observations, mean, standard deviation, median, minimum, and maximum. Categorical variables will be summarized by presenting the number of subjects and percentage for each category.

Summary results will be provided for each cohort and treatment group as well as overall.

All tabulations will be based on pooled data across centers.

Analyses will be performed using SAS for Windows statistical software, version 9.4 or higher (SAS, Cary, NC), except where other software may be deemed more appropriate.

CTI Clinical Trial and Consulting Services will perform all efficacy and safety statistical analyses.

Subject data will be listed, sorted by protocol, cohort, treatment group (number of VC02-300 units and ascending VC02-20/sentinel units [if applicable]), and subject number.

#### 4.1 Data Quality Assurance

ViaCyte Inc., or its designated representative, will conduct a pre-study visit for each study site to verify the qualifications of the investigator, inspect study site facilities, become familiarized with site staff assigned to the study, and inform the investigator of responsibilities and procedures for ensuring correct study documentation.

Data may be pulled by CTI Biostatistics for Data Safety Monitoring Board (DSMB) or interim analysis at a time when source verification and query resolution is ongoing.

All SAS programs used to create analysis datasets and output will be validated by ensuring that the ".log" files are void of all errors, warnings and notes indicative of problems. Additionally, each program will be checked to ensure that it performs according to the program specification. All programs are developed and validated by separate members of the CTI Biostatistics Department.

#### 4.2 Analysis Sets

The Full Analysis Set (FAS) is the intent-to-treat (ITT) set of subjects. This set is defined as all subjects who were enrolled into VC02-101 and received implantation of at least one VC-02-300 or sentinel unit on Study Day 1. Note that Cohort 1 in VC02-101 and in VC02-102 have no efficacy endpoints, so the subjects from Cohort 1 in VC02-101 and VC02-102 are not included in the FAS. All Cohort 2 VC02-101 efficacy summaries/analyses will be performed on the FAS. Subjects will be summarized by treatment group.

The Safety Analysis Set (SAS) will include all subjects from Cohort 1 and Cohort 2 who were enrolled into VC02-101 or VC02-102 and in whom an implant surgery was attempted, regardless of whether any VC-02-300 units or sentinel-sized units were actually implanted. The SAS will be used for safety summaries. All subjects enrolled in Protocol VC02-102 are part of Cohort 1.

#### 4.3 Assessment Windows

For the purpose of analyzing time to event endpoints, the time-in-study for each subject will be measured relative to Day 1, the day that the surgical procedure for VC-02-300 and/or sentinel unit implantation was attempted.

Study Visit	Target Study Day of Visit	SAP Windows		
Scheduled Study Visits for Cohort 1 and Cohort 2				
Week -4	-29	Day -36 to Day -23		
Week -3	-22	Day -22 to Day -1		
Day 1	1	Day 1		
Day 2	2	Day 2 to Day 3		
Week 2	15	Day 4 to Day 21		
Week 4	29	Day 22 to Day 42		
Week 8	57	Day 43 to Day 70		
Week 12	85	Day 71 to Day 98		
Week 16 (Cohort 1 Only)	113	Day 99 to Day 117		
Week 16 (Cohort 2 Only)	113	Day 99 to Day 126		
Week 17 (Follow-Up		Day 118 to Day 118+		
Visit: Cohort 1 Only)	120			
	Scheduled Study Visits for Col	nort 2 Only		
Week 20	141	Day 127 to Day 161		
Week 26	183	Day 162 to Day 228		
Week 39	274	Day 229 to Day 319		
Week 52	365	Day 320 to Day 410		
Week 65	456	Day 411 to Day 501		
Week 78	547	Day 502 to Day 592		
Week 91	638	Day 593 to Day 683		
Week 104	729	Day 684 to ∞		
Week 105 (Follow-Up Visit)	Last Date of Explantation + 7 Days	Not applicable		

Study visits will have windows as per the following schema:

The data will be summarized based on the electronic case report form (eCRF) (Study Visit) in which it was collected as long as the data is within the windows specified. If data for a particular Study Visit is not within the windows specified, then queries will be sent to the site to confirm data entry. ViaCyte will be notified of Study Visits that are not within the Study Visit Statistical Analysis Plan (SAP) windows. Data collected as an unscheduled visit will be re-assigned to a Study Visit based on the SAP visit windows specified.

Baseline will be defined as the last non-missing value prior to the start time of the surgical procedure for VC-02-300 and/or sentinel unit implantation, unless otherwise specified.

If more than one assessment exists within a single visit window (i.e., vital signs, laboratory samples, etc.), then the value taken closest to the target day of that visit will be used for analysis and summary purposes. In cases where two assessments are equally close to the target day, then

the first value will be used for analysis. Data from all assessments will be provided in the listing.

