The total duration of treatment (implantation) may be up to two (2) years for each Cohort 1 subject. Sentinels may be explanted at various time points post-implant to assess the status of cell viability and differentiation, vascularization, and the host response. The VC-02-300 unit(s) and all remaining sentinel units will be explanted at Visit 17/Week 104. Including the requirements of the screening period, Cohort 1 subjects will complete a total of 18 study visits spanning approximately 25 months as outlined in Table 1 – Schedule of Assessments. At a minimum, the first three (3) subjects in Cohort 1 will be enrolled sequentially in order to assess safety and tolerability data thru Week 2 before implanting the next subject. For example, data thru Week 2 from the first subject will be formally reviewed by the Sponsor prior to allowing the Investigator to implant the next subject. If a treatment-related SAE is observed within the first two weeks in the subject, the implantation of the next subject will be postponed until consultation between the Sponsor and Investigator has devised appropriate safeguards. Overall, if no treatment-related SAEs are observed with the first three (3) subjects after each has reached Week 4, additional Cohort 1 enrollment may then be performed in parallel.

A target minimum of three (3) evaluable subjects will be enrolled as part of Cohort 1, but up to 15 total subjects may be enrolled in Cohort 1 if the Sponsor and/or Data Safety Monitoring Board (DSMB) determine that additional subject data are necessary to properly evaluate the investigational product and/or the implantation procedure. After the minimum of three (3) subjects have been enrolled in Cohort 1 and have completed thru Week 4, the Sponsor then has the ability to initiate enrollment of Cohort 2 and request the DSMB to meet to review the cumulative Cohort 1 data for safety, tolerability, and proof of mechanism.

The DSMB will not meet regularly during Cohort 1 unless the Sponsor seeks an independent DSMB review based on Sponsor or Ethics Committee (EC) recommendations for managing AEs. The DSMB chair and/or the entire DSMB may receive regular updates as to the progress of the trial during Cohort 1.

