Cohort 1 subject. Sentinels and/or VC-02-300 units may be explanted at various time points postimplant to assess the status of cell viability and differentiation, vascularization, and the host response. Including the requirements of the screening period, Cohort 1 subjects will complete a total of 18 study visits spanning approximately 25 months. The total duration of treatment (implantation) may be up to four (4) months for each VC02-102 Cohort 1 subject. Sentinels may be explanted at various time points post-implant to assess the status of cell viability and differentiation, vascularization, and the host response. Any remaining units will be explanted at Week 16 (four months).

At the end of the treatment period for each subject enrolled under the VC02-101 and VC02-102 protocols, all remaining implanted units will be removed, and the subject will be required to participate in a separate, one-year, follow-up, non-interventional, observational study. The primary purpose of this additional study is to ensure there are no long-term safety issues associated with previous implantation with VC-02.

[figure not shown]

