#### 4.5 Multiple Comparisons

As this is a first-in-human study, there are no statistical hypotheses being tested.

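### SAP 4.3 gives VC02-101 Cohort 1 no visit window after Week 17, so its by-visit safety summaries from Week 20 to Week 104 have no defined handling

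*SAP*

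**What the plan says.** SAP 4.3 has two Week 16 rows. The Cohort 1 row runs from Day 99 to Day 117 and the Cohort 2 row from Day 99 to Day 126. The last Cohort 1 row is a Week 17 follow-up with target Day 120 and window "Day 118 to Day 118" plus, which I read as open-ended. All rows from Week 20 to Week 105 stand under a sub-header limited to Cohort 2. Week 105 has no window, by design.

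Three handling rules follow the table:
- Scheduled data are summarised under the eCRF visit "in which it was collected as long as the data is within the windows specified". Otherwise the site is queried and the sponsor is told.
- Unscheduled data are re-assigned to a visit by window.
- Where a window holds several values, the one nearest the target day is used.

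On follow-up of VC02-101 Cohort 1, Protocol 3.1 states: "The total duration of treatment (implantation) may be up to two (2) years for each Cohort 1" subject. SAP 3.2.3 states: "Cohort 1 subjects will complete a total of 18 study visits spanning approximately 25 months". Protocol 6 puts both cohorts on the same schedule. SAP Appendix 12.1.1 covers both VC02-101 cohorts in a single schedule to Week 105.

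**The concern.** The window table reflects a four-month Cohort 1, while the rest of both documents describes a two-year one. Cohort 1 exists to assess safety and tolerability, and its subjects are on immunosuppression. SAP 7.3 summarises laboratory data by visit, cohort and treatment group, with change from baseline where appropriate. SAP 7.4 summarises vital signs and their change from baseline at each visit. Under Table 1 of the protocol, hematology, chemistry and vital signs are all collected at every visit from Week 20 to Week 104. If the windows are followed literally, the SAP does not say how these Cohort 1 results enter the tables after Week 17. SAP 4.1 also allows data to be pulled for the DSMB while queries are still open, so a correctly dated visit could sit in query status when the board reviews it.

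**Working it through.** **Inputs.** Windows and target days come from SAP 4.3. Permitted visit ranges come from Protocol Table 1: ±7 days at Weeks 16, 20, 26 and 104, and ±14 days at Weeks 39 to 91.

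**Step 1: reproduce the target days.** Target day = 7 × week + 1. Week 16: 7 × 16 + 1 = 113. Week 17: 7 × 17 + 1 = 120. Week 20: 7 × 20 + 1 = 141. Week 104: 7 × 104 + 1 = 729. All agree with the SAP table.

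**Step 2: place each permitted range in the Cohort 1 rows and in the Cohort 2 rows.**

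| Visit | Permitted days | Cohort 1 row containing those days | Days from target to Day 120 | Cohort 2 row |
|---|---|---|---|---|
| Week 20 | 134–148 | Week 17 | 21 | 127–161 |
| Week 26 | 176–190 | Week 17 | 63 | 162–228 |
| Week 39 | 260–288 | Week 17 | 154 | 229–319 |
| Week 52 | 351–379 | Week 17 | 245 | 320–410 |
| Week 65 | 442–470 | Week 17 | 336 | 411–501 |
| Week 78 | 533–561 | Week 17 | 427 | 502–592 |
| Week 91 | 624–652 | Week 17 | 518 | 593–683 |
| Week 104 | 722–736 | Week 17 | 609 | 684 onward |

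None of the eight visits has its own Cohort 1 window. Under the Cohort 2 rows, which are contiguous, all eight fall in the right window over their whole permitted range.

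**Step 3: apply the rules.**
- *Scheduled data.* A Cohort 1 Week 26 visit on Day 183 carries a Week 26 eCRF label, but no Week 26 window applies to that cohort. It fails the condition and is queried. The site confirms a correct date, and the SAP gives no further instruction.
- *Unscheduled data.* A Cohort 1 unscheduled laboratory value on, say, Day 400 is assigned to Week 17, which is 400 − 120 = 280 days past that target. With the Cohort 2 rows it would go to Week 52 (Days 320 to 410). Protocol 6.17 foresees unscheduled visits for drug levels and for follow-up of abnormal laboratory results, so such values should be expected.

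**Step 4: Week 16.** The protocol allows Days 113 − 7 = 106 to 113 + 7 = 120. The Cohort 1 window ends at Day 117, so Days 118 to 120 (3 of the 15 permitted days) fall outside it. The Cohort 2 window, to Day 126, covers them.

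**Step 5: where the rows come from.** Under SAP 3.2.3 and Appendix 12.1.2, VC02-102 removes its last units at Week 16 and has a Week 17 follow-up. SAP 4.2 counts all VC02-102 subjects as Cohort 1. The Week 16 and Week 17 rows therefore fit VC02-102, and the label Cohort 1 extends them to VC02-101 subjects as well.

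**The case against.** A reader might infer that all Cohort 1 safety data after Week 16 collapse into one Week 17 window, with a single value per parameter surviving. The documents do not support that, for four reasons.

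- Most safety outputs do not use visit windows. Treatment-emergent events are defined by onset date (SAP 7.2.1) and counted per subject. Exposure uses implant and explant dates (SAP 7.1). Off-target growth and immune sensitization are per-subject incidences (SAP 7.6.1 and 7.6.2). Listings keep every assessment.
- Scheduled data are not moved by window. Only unscheduled data are, so collapse follows directly only for those. For scheduled data the fault is a missing rule, not deletion.
- The number of visits affected is eight, not nine, because Week 105 has no window by design. Early-termination safety data are pooled with Week 104 under SAP 4.6.8 without window mapping.
- Cohort 1 is small (3 to 15 subjects) and is outside the Full Analysis Set, so no efficacy result changes. SAP 4.5 adds: "As this is a first-in-human study, there are no statistical hypotheses being tested".

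It can also be said that a sensible programmer would simply apply the later rows to VC02-101 Cohort 1. That is likely, but the SAP labels those rows for the other cohort and nothing in it authorises the step.

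These points limit the scope. They do not remove the contradiction between the table and the two-year schedule.

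**Conclusion.** SAP 4.3 is wrong as written for VC02-101 Cohort 1. By-visit safety summaries at 8 of the 15 post-implant visits (Visits 10 to 17 out of Visits 4 to 18) have no applicable window and no rule beyond a query. Unscheduled values from Day 118 on map to a visit that is not on this cohort's schedule. Week 16 visits on Days 118 to 120 miss their window. The damage is limited to by-visit descriptive tables, chiefly laboratory data and vital signs with change from baseline.

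The conclusion assumes that the plus sign makes the Week 17 window open-ended and that the row labels are applied literally. If the window were Day 118 alone, unscheduled values after that day would have no window at all, and the gap for scheduled visits would be the same. The matter is modest in weight but should be corrected, because these tables describe long-term safety in the cohort enrolled to assess it.

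**What to change.** In SAP 4.3:
1. Relabel the Week 16 row ending at Day 117 and the Week 17 row as VC02-102 only.
2. Apply the Week 16 row ending at Day 126 and the rows from Week 20 to Week 105 to both VC02-101 cohorts, leaving Week 105 without a window.
3. Check the VC02-102 Week 16 row against that study's own schedule. Appendix 12.1.2 also allows ±7 days at Week 16, which reaches Day 120, so relabelling alone leaves the Day 117 mismatch there.

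It would also help to add one sentence saying how a scheduled visit is summarised once a query has confirmed an out-of-window date.

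The cost is an edit to one SAP table, with matching changes to any window programming. It needs no new data and no change to the visit schedule.

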#### ViaCyte Inc., Confidential

Protocol #VC02-101	V1 a Screen	V2 Screen	V3 Enroll	V4	V5	V6	V7	V8	V9	V10	V11	V12	V13	V14	V15	V16	V17 or ET	IAY 202 V18 Follow- Up
Assessments	Wk -5	Wk -4	Day 1	Day 2	Wk 2	Wk 4	Wk 8	Wk 12	Wk 16	Wk 20	Wk 26	Wk 39	Wk 52	Wk 65	Wk 78	Wk 91	Wk 104	Wk 105
2-hr MMTT/C-peptide & Glucose							X	Х	Х	Х		Х		Х		Х		
4-hr MMTT/C-peptide & Glucose		Х									X		Х		Х		Х	
Urinalysis	Х																	
Urine Albumin/Creatinine		Х									Х		Х		Х		Х	
Fasting Lipid Panel	Х										Х		Х				Х	
Immune Panel		Х				Х			Х		Х		Х				Х	
Reserve Blood Samples	Х										Х		Х		Х		Х	
Local Laboratory Tests				_														
Immunosuppression Drug Levels & Safety Panels							Х	(frequ	iency	as des	scribed	l in S e	ction '	7.11.3	)			
a. Pre-explant unit loca depending on anatom					t the di	scretion	of the	Invest	igator	. Uni	t locat	tion m	ay be	determ	ined v	ia pal	pation	
b. Video and/or photogr but are otherwise not			cal proc	edure	or impl	lantation	anato	mical l	ocatio	ons are	e to be	captu	red on	ly if r	equest	ed by	the Sp	onsor
c. A separate consent d	ocument	will be p	rovided	to the	e subjec	et for the	e follow	v-up st	udy.									
d. The Visit 1 drug scre provided kit.	en sampl	e will be	analyz	ed at t	the cent	ral lab.	The V	isit 3 d	lrug s	creen	is to b	e conc	lucted	locall	y usin	g the s	study-	
e. The urine pregnancy commences. Visit 17											s must	be av	ailable	e befor	e the	implan	it proc	edure
f. FSH testing only req	uired for	post-me	nopausa	l wom	en who	are not	using	contrac	eption	n.								
g. CMV IgM is not testo were negative.	ed at Visi	it 2 (only	IgG).	CMV	IgG an	d IgM te	sting i	s perfo	rmed	at Vis	it 13 a	and Vi	sit 17	only i:	f previ	ous te	st rest	ults
h. Ultrasensitive C-pep	tide samp	les to be	collecter	l in con	iunction	with MMT	Та ина а	timerratio	n (time	0)	1 /	· 1.	• • • • •	00		/ 10:	mutoc) ti	manint

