## 5.2. Immunosuppression Medications

An immunosuppressive regimen will be prescribed for each subject to facilitate the engraftment and long-term function of implanted VC-02 units. The overall regimen may include the following agents (\**Day 1 is Implant Day*):

- Induction (Cohort 1)
  - Basiliximab: Recommended course of 20 mg IV on Day 1 and Day 5. However, it may be administered as early as Visit 2 (Week -4).
- Induction (Cohort 2)

If data collected from Cohort 1 indicate sufficient engraftment and cell viability is achieved with basiliximab, its use will continue in Cohort 2. However, if data from Cohort 1 and/or data collected in subsequent subjects in Cohort 2 indicate insufficient cell viability is achieved, the following agent may be utilized:

- Anti-thymocyte globulin (ATG) recommended course:
  - Day -2 (0.5 mg/kg IV) required dose
  - Day -1 (1.0 mg/kg IV) required dose
  - Day 1 (1.5 mg/kg IV) required dose
  - Up to two additional 1.5 mg/kg/day IV doses of ATG may be administered (on Day 2, and/or Day 3). Prior to any additional dose administration of ATG, an absolute lymphocyte count (ALC) will be obtained locally. If the ALC has been reduced by at least 90% versus the pre-ATG administration level, additional dose(s) of ATG may not be required. The Investigator should contact the Sponsor to determine the need for additional dosing.

However, ATG may be administered using the above dosing schedule as early as Visit 2 (Week -4).

• Maintenance (both Cohorts)

The starting doses and target serum trough concentration levels listed below are recommendations. As determined by the Investigator and after consultation with the Sponsor, the doses and target trough levels may be adjusted.

- Mycophenolate mofetil (MMF): Recommended starting dose of 1 gm PO BID as early as Visit 2 (Week -4). Adjust the dose downward for gastrointestinal side effects. Mycophenolic acid (Myfortic) may be taken alternatively to alleviate such side effects. Trough level measurements for MMF are not required.
- Tacrolimus:

- If combined with MMF: Recommended starting dose of 2 mg PO BID as early as Visit 2 (Week -4); target serum trough concentration level of 10-12 ng/mL during the first three (3) months. Adjust the dose to maintain a serum trough concentration level of 7-9 ng/mL thereafter. Serum creatinine values should also be collected in conjunction with Tacrolimus trough levels in order to monitor for potential renal toxicity.

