- If combined with sirolimus and MMF: Recommended starting dose of 0.1 mg/kg per day in two (2) equal divided doses to achieve a target serum concentration of 6-8 ng/mL.
- Sirolimus: Recommended starting dose of 0.1 mg/kg/day as early as Visit 2 (Week -4); target serum trough concentration level of 8-10 ng/mL by at least Week -2 prior to implantation. Post-implant, target serum trough concentration levels of 12-15 ng/mL for the three (3) months after implantation and serum trough concentration levels of 10-12 ng/mL thereafter plus MMF (2 g/day).

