### 6.3. Visit 3 / Enrollment and Implantation (Day 1)

Subjects must be fasted for this visit. The following procedures will be completed:

- Ensure eligibility criteria continue to be met.
- Obtain weight/vitals.
- Perform an abbreviated PE.
- Obtain all laboratory samples per the Schedule of Assessments.
- Perform urine pregnancy test using the study-provided kit. Results must be available before the implant procedure commences.
- Collect and review CGM, SMBG, and diary data and verify subject has demonstrated compliance with diary entries; dispense additional supplies.
- Dispense immunosuppression drugs and provide instructions for dosing (as needed).
- Assess AEs and Concomitant Medications.
- Prepare subject for implantation.
- Implant VC-02-300 and sentinel units.
- Obtain video and/or photos of the implantation procedure (if requested by Sponsor).
- Dress the subject with the appropriate compression garments.

- Assess subject for up to four hours post-implantation for AEs.
- Remind subject to limit significant physical activity to ensure optimal healing at implantation sites. Instruct the subject on the proper use of all post-implant treatments.

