# 7.3 Clinical Laboratory Assessments

Laboratory assessments will be evaluated over time on study using descriptive statistics as described in Section 4.0. Clinical laboratory data will be summarized by study visit, cohort, and treatment group. Where appropriate, change from baseline in safety data will also be summarized in a similar manner.

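### For hematology, chemistry, vital signs and weight, change from baseline is measured from a Day 1 value that immunosuppressants may already have altered

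*SAP*

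**What the plan says.** The default baseline in SAP 4.3 is implant-based: "Baseline will be defined as the last non-missing value prior to the start time of the surgical procedure". It applies unless the SAP states otherwise. For laboratory data SAP 7.3 plans descriptive statistics by visit, cohort and treatment group, and adds: "Where appropriate, change from baseline in safety data will also be summarized in a similar manner". SAP 7.4 plans raw values and change from baseline for vital signs, including weight. Neither section names a different baseline.

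The Schedule of Assessments (Protocol Table 1; SAP Appendix A) marks hematology and chemistry at Visits 1, 2 and 3, and weight and vitals at every visit. For Visit 3, which is Day 1, Protocol 6.3 says "Obtain all laboratory samples per the Schedule of Assessments" ahead of the implant step. Protocol 6 also places vital signs and blood samples before implant procedures.

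Protocol 5.2 allows immunosuppression before that sample. For MMF it says "Recommended starting dose of 1 gm PO BID as early as Visit 2 (Week -4"); tacrolimus given with MMF may start equally early. Sirolimus may too, with "target serum trough concentration level of 8-10 ng/mL by at least Week -2 prior to implantation". ATG is an option in Cohort 2, with required doses on Day -2, Day -1 and Day 1, and the course may be moved as early as Visit 2. Cohort 1 induction is basiliximab, recommended on Day 1 and Day 5 but also allowed from Visit 2.

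**The concern.** The immunosuppressive regimen is part of the intervention, and its laboratory effects are among the things the safety tables should show. Protocol 5.2 asks for creatinine alongside tacrolimus troughs because of possible renal toxicity. Protocol 7.11 provides for local lymphocyte counts to confirm that suppression has been reached before the implant. A baseline taken after that intended effect removes some or all of it from the change column.

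The SAP treats other data differently. Its hypoglycemic-event, insulin and CGM baselines (SAP 4.6.3, 4.6.4, 4.6.6.1, 4.6.7) start at Day -3 and work backwards, and the SAP explains that day as the one before induction. Safety laboratory data and vital signs have no such provision.

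There is also a mixing problem. Treatment group means the number of VC-02-300 units first implanted, not the drug regimen, and the Protocol Summary says the regimen may vary between subjects. One change column can therefore combine subjects whose Day 1 value is drug-free with subjects whose Day 1 value is not.

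**Working it through.** The plan states no figure on this point, so there is nothing to reproduce. The check traces the rule through the schedule and then works out what it does to a change score.

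**1. Which parameters take Day 1 as baseline**

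| Parameter | Scheduled pre-implant measurements | Baseline under SAP 4.3 |
|---|---|---|
| Hematology, chemistry | Visits 1, 2, 3 | Day 1 |
| Vital signs, weight | Visits 1, 2, 3 | Day 1 |
| Fasting lipids | Visit 1 | Visit 1 |
| Urinalysis | Visit 1 (no later draw scheduled) | Visit 1 |
| Urine albumin/creatinine | Visit 2 | Visit 2 |

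**2. Exposure before the Day 1 sample**

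Maintenance drugs may start at Visit 2. That visit is nominally Week -4 and must be at least two weeks before Visit 3 (Protocol 6.2). Because the start is permitted rather than fixed, exposure runs from none to about four weeks. On the standard ATG schedule two doses (Day -2, Day -1) come before Day 1.

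**3. Effect on the change score**

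Set the untreated value to 100. Let f be the fraction left on Day 1 and g the fraction at a later visit.

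- Change from Day 1 = 100(g - f)
- Change from the untreated value = 100(g - 1)
- For a parameter the drugs lower, the effect is attenuated if g < f < 1, hidden if g = f, and reversed in sign if f < g < 1.

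Lymphocytes, with an assumed later value of 50 (g = 0.5), so that the change from untreated is 50 - 100 = -50 in every row:

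| Day 1 value (assumed) | Change from Day 1 | Reading |
|---|---|---|
| 10 | 50 - 10 = +40 (+400%) | reversed |
| 30 | 50 - 30 = +20 (+67%) | reversed |
| 50 | 50 - 50 = 0 | hidden |
| 80 | 50 - 80 = -30 (-38%) | attenuated |
| 100 | 50 - 100 = -50 (-50%) | correct |

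The first row uses a 90% fall. That number appears in Protocol 5.2 as a check before optional further ATG doses: "If the ALC has been reduced by at least 90% versus the pre-ATG administration level, additional dose(s) of ATG may not be required". Reaching it by Day 1 is an assumption here.

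Creatinine, assumed 0.90 mg/dL untreated and 1.20 later, so the change from untreated is +0.30:

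| Day 1 (assumed) | Change from Day 1 | Share of +0.30 shown |
|---|---|---|
| 0.95 | +0.25 | 83% |
| 1.05 | +0.15 | 50% |
| 1.20 | 0.00 | 0% |

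**4. Mixing**

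Take two subjects in one treatment group, both at 100 untreated and 50 later. If one is drug-free on Day 1 (100) and the other is at 10, their tabulated changes are -50 and +40. The mean is (-50 + 40)/2 = -5, although both fell by 50.

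**The case against.** The strongest reply is that the change column is only one of several planned displays. SAP 7.3 summarizes values by visit, and SAP 4.3 has separate windows for Week -4, Week -3 and Day 1, so a fall before implant should show in the visit means. All assessments are listed. Laboratory findings that meet Protocol 8.1.3 are adverse events, and SAP 7.2.7 tabulates treatment-emergent events by grade and by relationship to the regimen. An implant-based baseline also matches the treatment-emergent definition and isolates what happens after implantation. Finally, the Day -3 baselines reach back to Day -30 and may include maintenance drugs, so they precede induction but not necessarily all immunosuppression.

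Most of this stands, and it limits the point. A reader might infer that laboratory toxicity disappears from the planned output or that the DSMB would be misled. The documents do not support either: raw values remain, the DSMB reviews accumulated data, and its Charter is not available here. A reader might also infer that every safety laboratory test is affected, or that sign reversal applies to Cohort 1. The schedule rules out the first, and ATG is listed only as a conditional Cohort 2 option. The Cohort 1 primary endpoint counts adverse events and does not use laboratory change.

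The reply does not repair the change column itself. Visit means come from a shrinking set of subjects, since Protocol 10.3.2 plans a risk/benefit review at 9-12 months that can end participation. The within-subject change is the summary that allows for this, and its reference is the one in question. The adverse-event tables do not fill the gap fully, because events starting before implant surgery are not treatment-emergent and appear only in listings.

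**Conclusion.** The point holds for hematology, chemistry including creatinine and eGFR, vital signs and weight. Their default baseline normally falls on Day 1, when the regimen may already have acted, so change from baseline can attenuate or hide its effect. For lymphocytes in ATG-treated Cohort 2 subjects it can also reverse the sign.

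The size is unknown. The documents give no Day 1 or later laboratory values, and the illustrations rest on assumed ones. If no drug is started before the Day 1 sample, or the drugs have no effect by then, there is no distortion. The tables are descriptive, so no test, power figure or efficacy result is affected.

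A reader might conclude that the implant-based baseline is wrong and should be replaced. The documents do not compel that, since it answers a legitimate question about change after implantation. What is missing is a second reference. This is a cheap improvement worth making, and it leaves the rest of the safety analysis intact.

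**What to change.** In SAP 4.3, with cross-references in 7.3 and 7.4, add a pre-immunosuppression baseline for hematology, chemistry (including eGFR), vital signs and weight. Define it as the last non-missing value before the first dose of any study immunosuppressant, which will be Visit 1, or Visit 2 if taken before dosing. Derive it from dates, not visit labels, because the SAP 4.3 window table has no row for Visit 1 (Week -5). Report change from this baseline at each visit, show Day 1 as a visit row, and keep change from Day 1 as a second column for the implant effect.

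The cost is one derivation and one extra table column. The Visit 1 and Visit 2 measurements are already scheduled, and SAP 5.5 already lists medications by start date with immunosuppressants as a separate category. No sample, visit, dose or regimen changes.
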